Subjects who complete evaluations at Week 24 of the Treatment Phase will enter the Extension Phase. The Extension Phase is up to 104 weeks after the start of the study treatment, and subjects will receive an open-label E6011 200 mg every 2 weeks until Week 102. If the investigator or subinvestigator judges that the response to treatment is insufficient in the Extension Phase, administration of E6011 400 mg every 2 weeks will also be allowed (reduction of the dose back to 200 mg after an increase to 400 mg will also be allowed).

If subjects complete or discontinue the study, a follow-up visit should be conducted 28 days after the completion or discontinuation of the study, and a follow-up visit or telephone interview should be conducted 70 days after the last dosing.

An overview of the study design is presented below.

*: If the investigator or subinvestigator judges that response to treatment is insufficient during the Extension Phase, administration of E6011 400 mg every 2 weeks will also be allowed.

In addition, if subjects complete or discontinue the study, a follow-up visit should be conducted 28 days after the completion or discontinuation of the study, and a follow-up visit or telephone interview should be conducted 70 days after the last dosing.

Number of Subjects

A total of 175 subjects (25 for the 100 mg group, 50 for the 200 mg group, 50 for the 400 mg group, and 50 for the placebo group)

Inclusion Criteria

Subjects must meet all of the following criteria to participate in this study:

1. Aged ≥ 18 and < 75 years old at the time of written informed consent
2. RA patients who meet the 1987 ACR criteria or 2010 ACR/EULAR criteria ≥ 12 weeks before written informed consent
3. Received MTX treatment at 6 to 16 mg/week for ≥ 12 weeks before screening and presented ≥ 6 tender joints (out of 68 joints) and ≥ 6 swollen joints (out of 66 joints) in the Screening and Observation Phases
4. Able to continue a stable dose regimen of MTX at 6 to 16 mg/week from 4 weeks or more before starting the study treatment until completion of the Extension Phase (or until study discontinuation)
5. For patients with a history of biologics treatment for RA ^{Note}, the following criteria should be fulfilled.
(Note: This includes those treated in clinical studies)
 - The history of biologics treatment for RA with any of adalimumab, infliximab, golimumab, certolizumab pegol, etanercept, tocilizumab, and abatacept (including biosimilars).

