9.5.1.3.6 ASSESSMENT OF JOINT X-RAY

Joint x-ray images will be captured in the Screening Phase, Treatment Phase (Week 24), Extension Phase (Weeks 52, 76, and 104), and at discontinuation.

Joint x-ray images will be sent to the institute of joint x-ray central evaluation with subject identification number. The institute will evaluate the images, and the evaluation results of joint x-ray images captured by Week 24 will be submitted to the sponsor after unblinding. Joint x-ray images will be evaluated according to the separately prescribed procedures.

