5.3.5 Handling of Missing Data, Dropouts, and Outliers

For the efficacy analyses, approaches to handling missing data for continuous variables, except mTSS, will be the observed cases (OC) method and the last observation carried forward (LOCF) method; binary variables and EULAR response criteria will be the observed cases (OC) method, the last observation carried forward (LOCF) method and the non-responder imputation (NRI) method as each visit.

mTSS value at Week 24, Week 52 and Week 76 will be extrapolated from values of baseline and values of postbaseline, which will be used in summary statistics. The linear extrapolation method will be used for analysis of the structural progression endpoint (van der Heijde mTSS) to impute missing data at time points when analyses are conducted (including the analyses at Week 24, Week 52 and Week 76). For patients who discontinue the study or the study treatment or for patients who miss a radiograph for any reason, baseline data and the most recent radiographic data prior to discontinuation or the missed radiograph, adjusted for time, will be used for linear extrapolation to impute missing data at subsequent time points. All patients originally randomized to placebo will be switched to active treatment at Week 24; Missing postbaseline values will be imputed only if both a baseline value and a postbaseline value from another time point are available, as long as the patient was on the same treatment at each applicable time point.

Calculation for value of mTSS extrapolation will be derived by follow formula:

- Week 24 = (Postbaseline) + (Postbaseline – Baseline) * ((24 – (Study Day of Postbaseline / 7) / Study Day of Postbaseline / 7)
- Week 52 = (Postbaseline) + (Postbaseline – Baseline) * ((52 – (Study Day of Postbaseline / 7) / Study Day of Postbaseline / 7)
- Week 76 = (Postbaseline) + (Postbaseline – Baseline) * ((76 – (Study Day of Postbaseline / 7) / Study Day of Postbaseline / 7)

The two individual components of mTSS (Erosion and joint space narrowing [JSN] score) will be analyzed in the same way as the mTSS.

For the safety analyses for continuous value, descriptive statistics are used OC method and LOCF method, this is applied only the last observation of each phase, in tables and figures.

In the cases of laboratory result contains less (or more) than quantitation limit value is treated as:

- a. zero, when less than quantitation limit value,

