5.4.2 Secondary Efficacy Analyses

For each component of ACR (TJC, SJC, VAS [patient's assessment of pain, patient's global

assessment of disease activity and physician's global assessment of disease activity], functional assessment by subjects (HAQ) and CRP·ESR), DAS28-ESR, DAS28-CRP, SDAI, and CDAI in each visit, the values and the changes from baseline will be summarized by treatment group.

For mTSS, values and changes from baseline will be summarized by treatment group. For DAS28-ESR and DAS28-CRP, frequency and percentage of each classification (no response, moderate response, good response) by EULAR response criteria will be summarized by treatment group and visit in a shift table. For DAS28-ESR, DAS28-CRP, SDAI and CDAI, frequency and percentage of each category (Remission, Low, Moderate, High) will be summarized by treatment group and visit in a shift table.

The mean change from baseline of ACR components, DAS28-CRP, DAS28-ESR, CDAI and SDAI - visit will be displayed by treatment group. ACR response rate - visit will be displayed by treatment group. Cumulative probability of the change from baseline in mTSS will be displayed at week 52 and Week 76.

All efficacy endpoints for the treated subjects will be listed.

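### A missed Week 52 joint film is extrapolated from the baseline-to-Week 24 slope even when a Week 76 film exists (eligible E6011 subjects, descriptive output only)

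*SAP*

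**What the plan says.** Protocol 9.5.1.3.6 sets the film schedule: "Joint x-ray images will be captured in the Screening Phase, Treatment Phase (Week 24), Extension Phase (Weeks 52, 76, and 104), and at discontinuation". The film before Week 52 is Week 24 and the film after it is Week 76.

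SAP 5.3.5 takes mTSS out of the observed-case and LOCF methods used for the other continuous variables and gives it a linear rule. The rule covers subjects who discontinue and also applies "for patients who miss a radiograph for any reason". In both cases "baseline data and the most recent radiographic data prior to discontinuation or the missed radiograph, adjusted for time, will be used for linear extrapolation". The Week 52 formula is printed as "Week 52 = (Postbaseline) + (Postbaseline – Baseline) * ((52 – (Study Day of Postbaseline / 7) / Study Day of Postbaseline / 7". Erosion and joint space narrowing scores are handled the same way. Nothing in the SAP provides for interpolation between two films.

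Two sentences in the same section limit the rule. One says "All patients originally randomized to placebo will be switched to active treatment at Week 24". The other allows imputation only "as long as the patient was on the same treatment at each applicable time point". The SAP does not define what counts as the same treatment.

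The results feed descriptive output in SAP 5.4.2: mTSS values and changes by treatment group, and a plot: "Cumulative probability of the change from baseline in mTSS will be displayed at week 52 and Week 76".

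**The concern.** Extrapolation is a natural choice after a subject's last film, because nothing later exists. A subject who misses only Week 52 has films on both sides of the gap. Using only the earlier side discards information already read and multiplies the error in the Week 24 change by 52/24. It can also produce a Week 52 score above the score the same subject shows at Week 76.

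The later film should usually exist for subjects still in the study. Protocol section 7 says the last subject entered the Extension Phase in March 2018. Entry is at Week 24, so 52 weeks later is Week 76, reached by March 2019.

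At stake are the Week 52 mTSS, erosion and joint space narrowing summaries and the tails of the Week 52 cumulative probability plot, where a few extreme values can show. Because mTSS is exempt from the observed-case method, no alternative mTSS summary is specified that would reveal such values.

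**Working it through.** The plan states no figure for this rule, so there is none to reproduce.

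**Inputs.** Films at baseline (B), Week 24 (P) and Week 76 (L), from Protocol 9.5.1.3.6. The printed Week 52 formula has unbalanced brackets. I read it as intended: P + (P − B) × (52 − w)/w, with w = study day/7. Baseline counts as week 0, as the formula implies. Assumption: each film carries independent error with the same variance s².

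1. **The two estimates at w = 24.**
   - As planned: B + (P − B) × 52/24, that is 2.167 P − 1.167 B.
   - Interpolated: P + (28/52)(L − P), that is 0.462 P + 0.538 L.

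2. **Error variance of the imputed Week 52 change, linear progression.**
   - As planned: 2 × (52/24)² = 9.39 s².
   - Interpolated: (24/52)² + (28/52)² + 1 = 0.213 + 0.290 + 1 = 1.50 s².
   - Observed change: 1 + 1 = 2.0 s².
   - Ratio of planned to interpolated: 6.2 in variance, 2.5 in SD.

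3. **Error SD of the imputed Week 52 score, same model.**
   - As planned: √(2.167² + 1.167²) = 2.46 s.
   - Interpolated: √(0.462² + 0.538²) = 0.71 s.
   - SD ratio: 3.47.

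4. **Sensitivity: no film error, progression a random walk with variance t² per week.**
   - As planned: 28 + (28/24)² × 24 = 60.67 t².
   - Interpolated: 28 × 24/52 = 12.92 t².
   - Variance ratio 4.69, SD ratio 2.17. Mixtures of the two error sources lie between 2.17 and 3.47.

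5. **When the imputed Week 52 score passes the observed Week 76 score.** From Week 24 the projection adds 28 × early weekly rate. The subject's real change to Week 76 is 52 × later weekly rate. With a positive early change, the projection is higher when the later rate is below 28/52 = 54% of the early rate.

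6. **Example.** Changes from baseline of +2.0 at Week 24 and +2.5 at Week 76:
   - As planned at Week 52: 2.0 × 52/24 = +4.33.
   - Interpolated: 2.0 + 0.5 × 28/52 = +2.27.

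7. **Who is in scope.** Planned sizes are "25 for the 100 mg group, 50 for the 200 mg group, 50 for the 400 mg group, and 50 for the placebo group", 175 in all. Placebo subjects fail the same-treatment condition because of the Week 24 switch. Protocol 9.4.1 gives the dose history of the rest.
   - Same treatment means any E6011: 25 + 50 + 50 = 125.
   - Same dose at Weeks 24 and 52: 50 + 50 = 100, because the 400 mg arm is on 200 mg from Week 12 and the 100 mg arm moves to 200 mg at Week 24.
   - Same dose throughout: 50, the 200 mg arm only.
   - Escalation to 400 mg in the Extension Phase may remove more.

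**The case against.** **The effect on reported results may be negligible.** Only eligible subjects with Week 24 and Week 76 films and no Week 52 film matter. As an assumed illustration, take 2 such subjects in an arm of 50. The average error variance of the change is (48 × 2.0 + 2 × 9.39)/50 = 2.30 s² against 2.0 s², about 7% in SD, before real differences between subjects dilute it. This stands: the large ratios describe single imputed values, not the group mean or SD. A visible effect is plausible only in the tails of the plot.

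**The example assumes a sharp slowing.** Its later rate is 88% below its early rate, which is not the linear course used for the variances. This is fair; the example shows what the rule can do, not what is typical. Exceeding the Week 76 score is also not proof of error. In a simulation with linear progression of one film-error SD per 24 weeks, the extrapolated value exceeded Week 76 in 35% of cases, but a real Week 52 film did so in 24%. A reader might infer that the planned values are contradicted by later films; that is too strong.

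**Interpolation is smoother than data.** Its error variance (1.5 s²) is below that of an observed change (2.0 s²), so the Week 52 spread may be slightly understated. This stands as a small cost.

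**The SAP may already admit a later film.** The section requires a postbaseline value from another time point. That is a condition for imputing at all; the film used is fixed by the earlier sentence as the one before the gap. Putting Week 76 into the formula would not help: 2.5 × 52/76 = +1.71, below the +2.0 already seen at Week 24.

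**Conclusion.** The point holds in a limited form. For eligible E6011 subjects, SAP 5.3.5 as written ignores an available Week 76 film when Week 52 is missed. The resulting score has roughly 2.2 to 3.5 times the error SD of an interpolated one. That range rests on an assumed error model, since the documents give no mTSS variability.

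Three stronger readings are not supported:

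- *That every missed Week 52 film is affected.* The same-treatment condition excludes the 50 planned placebo subjects and leaves 125, 100 or 50 planned subjects, and only those with the bracketed gap count.
- *That the trial's radiographic or efficacy conclusions are at risk.* The radiographic objective is at Week 24 and the primary endpoint at Week 12. SAP 5.3.2, 5.3.3 and 5.4.1 plan no covariates, multiplicity adjustment or primary efficacy analysis for the Extension Phase.
- *That such gaps will be common because Table 8.12 dates Week 52 at +334 days instead of 52 × 7 = 364.* That could make on-time films look missing, but it is a separate error with its own repair and adds no weight here.

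The number of affected subjects is not given and is probably small. Low priority, worth doing because it is nearly free.

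**What to change.** Add to SAP 5.3.5:

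*A missing film lying between two available films is imputed by linear interpolation on actual film dates between the nearest earlier and later films, provided the same-treatment condition below holds at all three time points; extrapolation is used only after the last available film.*

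State what same treatment means for this purpose: any E6011, the same dose at the films concerned, or the same dose throughout. Say also how subjects escalated in the Extension Phase are classed. Under the proposed condition, placebo-randomised subjects remain unimputed at Week 52, as now. Apply the rule to the erosion and joint space narrowing scores.

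The cost is one sentence, one definition and a small program change, using films already read. The two methods agree when progression is exactly linear and free of error. The only statistical drawback is the slight understatement of Week 52 spread noted above.

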3 INTRODUCTION

The purpose of this statistical analysis plan (SAP) is to describe the procedures and the statistical methods that will be used to analyze and report results for Eisai Protocol E6011-J081-201. Since the Version 6 of the protocol defined that it was unnecessary to conduct assessments other than safety assessment, all the efficacy analysis will be conducted until Week 84, that is the latest Visit of ongoing subjects at the time of amendment of the protocol.

Statistical methods of Extension Phase are provided in this document.

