5.1.2 Secondary Endpoints

- ACR20, ACR50, and ACR70 response rate at each visit (excluding ACR20 at Week 12)
- Values and change from baseline in ACR components (TJC, SJC, VAS [patient's assessment of pain, patient's global assessment of disease activity and physician's global assessment of disease activity], functional assessment by subjects [HAQ-DI], and CRP·ESR), DAS28-ESR, DAS28-CRP, SDAI, and CDAI at each visit
- EULAR response criteria at each visit; subjects will be classified based on DAS28-ESR or DAS28-CRP
- DAS28-ESR, DAS28-CRP, SDAI, CDAI, and Boolean remission rates at each visit
- Values and change from baseline in modified total sharp score (mTSS) at each visit

The ACR50 response is defined similar to the ACR20 with a 50% reduction.

The ACR70 response is defined similar to the ACR20 with a 70% reduction.

The DAS28-CRP calculates on the following formula, and disease activity is categorized as High at > 4.1 , Moderate at > 2.7 and ≤ 4.1 , Low at ≤ 2.7 , and Remission at ≤ 2.3 .

$$0.56 \times \text{sqrt}\{\text{TJC in 28 joints (TJC28)}\} + 0.28 \times \text{sqrt}\{\text{SJC in 28 joints (SJC28)}\} + 0.36 \times \ln\{\text{CRP (mg/dL)} \times 10 + 1\} + 0.014 \times \text{Patient's Global Assessment of Disease Activity (VAS) (mm)} + 0.96$$

The DAS28-ESR will be calculated on the following formula, and disease activity is categorized as High at > 5.1 , Moderate at > 3.2 and ≤ 5.1 , Low at ≤ 3.2 , and Remission at < 2.6 .

$$0.56 \times \text{sqrt}\{\text{TJC28}\} + 0.28 \times \text{sqrt}\{\text{SJC28}\} + 0.70 \times \ln\{\text{ESR (mm/h)}\} + 0.014 \times \text{Patient's Global Assessment of Disease Activity (VAS) (mm)}$$

EULAR Response Criteria:

Present DAS28	DAS28 change from baseline		
	<-1.2	≥ -1.2 and <-0.6	≥ -0.6 (missing included)
Low	Good response	Moderate response	No response
Moderate	Moderate response	Moderate response	No response
High	Moderate response	No response	No response

The CDAI will be calculated on the following formula, and disease activity is categorized as High at > 22 , Moderate at > 10 and ≤ 22 , Low at ≤ 10 , and Remission at ≤ 2.8 .

$$\begin{aligned} & \text{SJC28} + \text{TJC28} \\ & + \text{Patient's Global Assessment of Disease Activity (VAS) (mm)/10} \\ & + \text{Physician's Global Assessment of Disease Activity (VAS) (mm)/10} \end{aligned}$$

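### The mTSS extrapolation formulas printed in SAP 5.3.5 have unbalanced brackets and do not express the linear extrapolation that the section prescribes

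*SAP*

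**What the plan says.** The SAP covers the open-label part of the trial: "Statistical methods of Extension Phase are provided in this document". Section 5.1.2 lists as a secondary endpoint "Values and change from baseline in modified total sharp score (mTSS) at each visit", and section 5.4.2 states "For mTSS, values and changes from baseline will be summarized by treatment group". Section 5.4.2 also plans cumulative-probability displays of the change at Weeks 52 and 76.

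For missing films, section 5.3.5 says that "baseline data and the most recent radiographic data prior to discontinuation or the missed radiograph, adjusted for time, will be used for linear extrapolation". It then announces "Calculation for value of mTSS extrapolation will be derived by follow formula" and prints one line each for Weeks 24, 52 and 76. The multiplier in the Week 52 line has as its core "52 – (Study Day of Postbaseline / 7) / Study Day of Postbaseline / 7", preceded by two opening brackets and followed by one closing bracket. The other two lines differ only in the week number.

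The imputed scores are derived from baseline and "values of postbaseline, which will be used in summary statistics". The erosion and joint space narrowing (JSN) scores follow the same rule. Imputation is limited to patients who were on the same treatment at each time point involved.

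The Protocol, section 9.5.1.3.6, sets the film schedule: "Joint x-ray images will be captured in the Screening Phase, Treatment Phase (Week 24), Extension Phase (Weeks 52, 76, and 104), and at discontinuation".

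**The concern.** The printed lines are the operative imputation rule for a listed secondary endpoint and its two components, and they do not yield the method named in the sentences around them. The missing closing bracket is easy to see. The unbracketed final divisor is easier to overlook, and supplying only the first leaves a formula that runs without error and returns plausible scores.

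Those scores would be almost the same as the last film carried forward. Section 5.3.5 uses observed cases and last observation carried forward for continuous variables but exempts mTSS from both, so the faulty version would in effect bring back a method that the section sets aside for this endpoint. Progression after the last film would nearly vanish for the imputed patients. Linear extrapolation is the only missing-data method named for mTSS, so no parallel planned analysis would expose the error.

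**Working it through.** The documents contain no worked mTSS value to reproduce, so the check is algebraic.

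**Notation.** T is the target week, D the study day of the last film, w = D/7 the film time in weeks, and Post and Base the two observed scores.

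**Intended rule.** A straight line from baseline at week 0 through the film at week w gives, at week T,

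Post + (Post − Base) × (T − w)/w.

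**Printed multiplier.** In this notation it is `((T − (D/7) / D / 7)`: three opening brackets and two closing. It does not parse.

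**Adding one closing bracket.** Evaluated at every possible position, with division taken left to right, only three distinct values result:

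- Closing after the first division by 7, `((T − (D/7)) / D / 7)`, gives (T − D/7)/(7D) = (T − w)/(49w). This is exactly 1/49 of the intended multiplier. (Closing directly after the first D gives the same value.)
- Closing at the end, or directly after T, gives T − 1/49, which is 51.98 for Week 52.
- Closing after the second D gives (T − 1/7)/7, which is 7.41 for Week 52.

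The last two do not depend on when the film was taken, so they contradict the time adjustment in the prose. None of the three is linear extrapolation. Under literal evaluation the smallest correction is three bracket characters: one to close the first group, and a pair around the final D/7.

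**Size of the 1/49 version.** The table takes an observed change from baseline of 1.0. Total change is 1 plus the multiplier.

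| Last film → target | Intended multiplier | One-bracket multiplier | Intended total | One-bracket total | Ratio of totals |
|---|---|---|---|---|---|
| Week 24 → 52 | 28/24 = 1.1667 | 0.0238 | 2.17 | 1.02 | 0.473 |
| Week 40 → 52 | 12/40 = 0.3000 | 0.0061 | 1.30 | 1.006 | 0.774 |
| Week 24 → 76 | 52/24 = 2.1667 | 0.0442 | 3.17 | 1.04 | 0.330 |
| Week 40 → 76 | 36/40 = 0.9000 | 0.0184 | 1.90 | 1.018 | 0.536 |
| Week 52 → 76 | 24/52 = 0.4615 | 0.0094 | 1.46 | 1.01 | 0.691 |
| Week 64 → 76 | 12/64 = 0.1875 | 0.0038 | 1.19 | 1.004 | 0.845 |

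Weeks 24 and 52 are scheduled films. Weeks 40 and 64 are assumed dates for a film at discontinuation.

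**Origin of time.** Study day is not defined for this formula. SAP 5.6 sets Day 1 at first dose for safety analyses, and Table 8.1 labels first dose + 28 days as Day 29. On that count an on-time Week 24 film is Day 169, so w = 169/7 = 24.14 and the Week 52 multiplier is 1.154 instead of 1.167, a difference of −1.1%.

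The baseline film is a screening film, taken up to 42 days before first dose. At that extreme the film-to-film interval to Week 24 is 24 + 6 = 30 weeks and the multiplier is 28/30 = 0.93, which is 20% below 1.17. The intended figures in the table therefore assume baseline at Week 0, as in Table 8.12.

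**The case against.** The strongest reply is that the method is fully specified and only the notation is faulty. The prose names linear extrapolation, the two films and the time adjustment. The study-day-over-seven term appears twice in each line, the first time bracketed as one quantity. A reader who treats the second occurrence the same way needs only the missing closing bracket and reaches the right answer. This stands: the 1/49 result belongs to literal left-to-right coding, not to every sensible reading.

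Three further limits also stand.

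- The same-treatment condition narrows who is imputed. On a plain reading, subjects randomized to placebo (50 of 175 planned), who switch to E6011 at Week 24, get no later value from a baseline-to-Week-24 slope. If the same treatment means the same dose, the 100 mg and 400 mg groups may be affected too, because their planned doses change at Week 24 and Week 12 respectively.
- The largest shortfall, 33% of the intended total for Week 24 to Week 76, arises only if there is no film at Week 52, at Week 76 or at discontinuation. A discontinuation film is scheduled, so this should be unusual.
- The Week 24 line has little scope here. The SAP's full analysis set requires dosing after Week 24, and no postbaseline film is scheduled before Week 24 except at discontinuation.

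The reply does not remove the defect. The SAP offers these lines as the rule, the same fault stands in all three (so a fault in reading the PDF is unlikely, though not excluded), and neither document gives a corrected version.

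**Conclusion.** Wrong as written; minor. The three formulas cannot be evaluated as printed and do not express the linear extrapolation that the section prescribes, although the intent can be recovered from the prose. The 1/49 increment rests on two assumptions: that only the missing closing bracket is supplied, and that division runs left to right. In the six cases shown, the total change would then be 33% to 85% of the intended total, with the smaller shortfalls where the last film lies closer to the target week.

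A reader might infer that the reported mTSS results are wrong, or that progression was understated about fiftyfold. The documents do not support this. SAP section 9 places the programming rules in separate documents that are not available here, and the factor applies to the imputed increment only, not to observed scores or to the total change. Nor can an effect on group means be stated, because the number of missing films is not given. The outputs concerned are descriptive Extension Phase summaries and cumulative-probability displays. The Week 12 ACR20 analysis is not touched.

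**What to change.** For T = 24, 52 and 76, and for mTSS, erosion and JSN alike, print:

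`Week T = Post + (Post − Base) * ((T − D/7) / (D/7))`

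Define D as days from first dose to the film (study day minus 1 if the first dose is Day 1). State that baseline is placed at Week 0, as in Table 8.12, although the baseline film is a screening film. Then check the programmed derivation against this line. One hand-calculated patient is enough to tell it from the 1/49 version: a film at D = 168 with an observed change of 1.0 must give 2.17 at Week 52, not 1.02.

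The cost is three lines of text, one definition and one code check, with no new data. Protocol 9.7.5 already provides for documenting an SAP revision and describing it in the clinical study report.
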